4 STUDY DESIGN

The trial design is a single-site, two-arm, parallel-group, participant-blinded, randomized, placebo-controlled, two-sided comparative study, with an internal pilot study for blinded sample size re-estimation. Allocation to study arm will be by block randomization stratified by sex within cohort (semester) with a 1:1 allocation ratio.

5 STUDY POPULATION

5.1 STUDY SETTING

The study will take place at Ross University School of Veterinary Medicine (RUSVM) on the island of St Kitts in the Caribbean. The Doctor of Veterinary Medicine (DVM) program at RUSVM comprises a preclinical curriculum of seven semesters in St Kitts, and three semesters of clinical training at an affiliated school of veterinary medicine in the United

States, Canada, or other international location. There are three semesters per year (starting in January, May and September), and one intake (cohort) per semester. Each semester is 15 weeks, with a break of two or three weeks between semesters. RUSVM also offers a one-semester Veterinary Preparatory (VP) program. Students who successfully complete the VP program are placed into first semester classes. The study will enroll participants from the VP program and the 1st and 5th semester classes of the DVM program each semester.

Because St Kitts is free from rabies (<https://www.cdc.gov/importation/rabies-free-countries.html>), students are not required to receive pre-exposure rabies prophylaxis during their preclinical training (semesters 1-7). All students at RUSVM must have received a primary course of rabies vaccine before the end of their preclinical program to provide cover during their clinical training (semesters 8-10). This is based on the recommendations of the Advisory Committee on Immunization Practices for human rabies prevention [15], that veterinarians in the United States are considered a population in the “frequent” risk category for rabies exposure, for whom the pre-exposure recommendations are (i) primary course of rabies vaccine, followed by (ii) serological testing every two years, and (iii) booster vaccination if antibody titer is below acceptable level. Students who have not received a primary course of rabies vaccine by their 7th semester are able to do so through RUSVM Student Health Services, at a current cost of US\$ 200 for the 3-dose course. Vaccinations are done by the RUSVM Student Health Services using Rabivax-S, produced by the Serum Institute of India Pvt. Ltd (SIIPL).

5.2 ELIGIBILITY CRITERIA

5.2.1 INCLUSION CRITERIA

A student registered at RUSVM will be eligible for inclusion in the study if s/he is in the VP program or the 1st or 5th semester of the DVM program.

5.2.2 EXCLUSION CRITERIA

A student registered at RUSVM and in the VP program or the 1st or 5th semester of the DVM program will be excluded from the study if s/he:

- 1) has previously received a dose of rabies vaccine, or
- 2) is intending to undertake activities during the course of participation in the study that would increase their risk category of rabies exposure above that of the U.S. population at large, as defined by the Advisory Committee on Immunization Practices (ACIP) for human rabies prevention [15], or
- 3) does not provide informed consent for participation, or
- 4) enrolls in the study but does not present for the first injection within the first 12 weeks of the semester (up to and including Week 12), or
- 5) has a contraindication to rabies vaccine as described in the Rabivax-S package insert (see **Section 5.2.3, Screen Failures** for details).

5.2.3 SCREEN FAILURES

Eligible students who consent to participate in the study and who present for the first injection within the first 12 weeks of the semester will be screened by study personnel at the RUSVM Student Health Services for contraindications to the vaccine, prior to

assignment to study intervention. Contraindications are described in the vaccine package insert and are defined as follows:

1. Contraindications requiring postponement of vaccination:
 - a. Fever or an acute illness
 - b. Antimalarial medication or other short-term immunosuppressive treatments
 - c. Pregnancy
 - d. Breastfeeding
2. Absolute contraindications:
 - a. Known systemic hypersensitivity to any of the vaccine components
(including neomycin)
 - b. History of life-threatening reaction to a vaccine containing any of the same substances as Rabivax-S

Individuals who fail screening because of a contraindication requiring postponement of vaccination may be rescreened once the condition is resolved, so long as they still meet the inclusion criteria for the study (a student in the VP program or the 1st or 5th semester of the DVM program) and that the intervention regimen (3-dose course on Days 0, 7 and 21) could still be completed before the semester break (to comply with this requirement, the latest time at which an individual could be rescreened is in Week 12 of the semester).

Individuals who fail screening because of an absolute contraindication will be excluded from the study.

6 STUDY INTERVENTIONS

6.1 VACCINE GROUP

The study intervention is at least one dose (1 mL by intramuscular injection) of a three dose primary course of Rabivax-S. Rabivax-S is a lyophilized vaccine manufactured by Serum Institute of India Pvt. Ltd. containing inactivated purified rabies antigen (Pitman Moore, PM3218 as virus strain) produced using Vero ATCC CCL 81 cells. The diluent (sterile water for injection) is provided in a separate 1 mL ampoule. After reconstitution, a single dose of 1 mL contains an inactivated, purified rabies antigen (not less than 2.5 IU), glycine (40 mg), sucrose (40 mg) and human serum albumin (25% 10 mg).

6.2 CONTROL GROUP

The intervention (placebo) in the control group is at least one dose (1 mL by intramuscular injection) of a three dose primary course (on days 0, 7 and 21) of vaccine diluent (sterile water for injection).

6.3 DOSING AND ADMINISTRATION

Dosing and administration of the vaccine (Rabivax-S) will be according to the package insert, following the schedule for pre-exposure prophylaxis via the intramuscular route; that is, 1 mL by intramuscular injection in the deltoid area of the arm on Day 0, Day 7 and Day 21. Dosage and administration of the placebo (sterile water for injection) will follow the same schedule and route of administration; that is, 1 mL by intramuscular injection in the deltoid area of the arm on Day 0, Day 7 and Day 21. In the event of interruption of the schedule of administration (of either the vaccine or the placebo), the schedule will be

resumed without repeating a previous dose (as per Table 3 Recommendations for Interrupted or Delayed Routine Immunization – Summary of WHO Position Papers, updated April 2018; http://www.who.int/immunization/policy/immunization_tables/en/).

Vaccine and placebo will be administered to participants at the RUSVM Student Health Services by study nurses or nurse practitioner, using a 25G (0.50 x 25mm) needle and 2 mL syringe.

6.4 STUDY INTERVENTION COMPLIANCE

The number of doses received, and the date received, will be recorded by study personnel at RUSVM Student Health Services in Case Report Forms (CRF) for Visits 1-3. An entry will also be made in students' health records at RUSVM Student Health Services.

6.5 DISCONTINUATION OF STUDY INTERVENTION

Prior to administration of each dose of either the vaccine or placebo, participants will be assessed by personnel at the RUSVM Student Health Services for contraindications to the vaccine (see **Section 5.2.3, Screen Failures** for listed contraindications). Individuals with a contraindication requiring postponement of vaccination may return once the condition is resolved to resume the intervention for their allocated group (vaccine or placebo), so long as this occurs before study completion (see **Section 7, Participant Timeline** for definition of study completion). In the event of interruption of the schedule of administration (of

either the intervention or the control), the schedule will be resumed without repeating a previous dose (see **Section 6.3, Dosing and Administration** for details).

Participants for whom the study intervention was halted, due to absolute contraindications or other clinically-relevant event, or for whom intervention was postponed beyond the time of study completion, will remain in the study and complete the weekly illness surveys.

7 PARTICIPANT TIMELINE

Students will be informed about the trial prior to the start of the semester for which they are eligible (orientation week for VP and 1st semester cohorts, and at the end of 4th semester for 5th semester cohorts). Students will be recruited into the study during orientation week and/or the first week of the semester, and will receive the first injection (day 0) within the first two weeks of the semester. Participants will receive the second injection on day 7 and the third injection on day 21. If necessary, participants can begin the intervention later, so long as day 0 falls within the first 12 weeks of the semester (see **Section 5.2.2, Exclusion criteria** for details).

Weekly illness surveys will begin in study week 3 (Monday of study week 3, day 10-14 after first injection) for all participants, and will continue for 26 weeks (through week 11 of the following semester in the case of a two-week semester break, or week 10 of the following semester in the case of a three-week semester break). One week after receipt of the final (26th) weekly survey, participants will be unmasked and will exit the study. Following exit, participants who were allocated to the control group will begin a primary course of rabies

vaccine in weeks 11 or 12 (depending on 3- or 2-week semester break), to be completed by the end of the semester (weeks 14 or 15).

A participant is considered to have completed the study one week after receipt of the final (26th) weekly survey.

7.1 PARTICIPANT DISCONTINUATION/WITHDRAWAL FROM THE STUDY

Participants are free to withdraw from participation in the study at any time upon request.

Participants who fail to complete surveys for three consecutive weeks will be followed up and contacted to determine if they have withdrawn or wish to withdraw from the study. If so, they will be informed of their rabies vaccination status and withdrawn from the study.

Participants will also be withdrawn from the study if for any reason they become aware of their study arm allocation (unblinding). The reason for participant withdrawal will be captured in the End of Study CRF.

Schedule of activities for participants in a single cohort (semester)

Weeks since allocation (Study week)	Weeks of semester/break	1 st semester						Semester break*		2 nd semester					
		Wk-1	Wk1	Wk2	Wk3	Wk4	Etc.	Wk15	Wk16	Wk17	Etc.	Wk25	Wk26	Wk27	Wk28
		Wk1	Wk2	Wk3	Wk4	Wk5	Etc.	Wk1	Wk2	Wk1	Etc.	Wk8	Wk9	Wk10	Wk11
ENROLLMENT															
Information		X	X												
Eligibility screen		X	X												
Informed consent		X	X												
Contraindication screening				X											
Allocation				X											
INTERVENTION**															
Dose 1				X											
Dose 2					X										
Dose 3						X									
ASSESSMENTS															
Baseline			X												
Weekly illness survey (1-26)					X (S1)	X (S2)	X (Etc.)	X (S13)	X (S14)	X (S15)	X (Etc.)	X (S23)	X (S24)	X (S25)	X (S26)
Solicited adverse events			X	X		X									
Unsolicited adverse events			X	X	X	X									
Blood collection (efficacy ancillary study)		X (D-7)										X (D180)			
Blood collection (immunology ancillary study)			X (D0)			X (D21)		X (D90)							
Study exit															X

*Some semester breaks are three weeks long, in which case Weeks 27 and 28 since allocation will fall in Weeks 9 and 10 of 6th semester

**Schedule shown here assumes administration of the first dose in week 2 and administration of subsequent doses per schedule (day 7 and day 21). If necessary, participants can begin the intervention at any time in the first 12 weeks of the semester.

7.2 LOST TO FOLLOW-UP

A participant will be considered lost to follow-up if s/he fails to complete a weekly survey for more than three consecutive weeks and is unable to be contacted by the study personnel. Contact will be by email to the participant's registered RUSVM email address. The participant will be considered unreachable if s/he does not respond after 3 emails. At this point, s/he will be considered to have withdrawn from the study with a primary reason of lost to follow-up.

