12 DATA COLLECTION METHODS

After enrollment, participants will complete a questionnaire that will capture data on relevant baseline characteristics including sex, age, health and vaccination status. (Baseline CRF; Appendix C). Participants will complete a short survey each week, starting in study week 3, to capture self-reported episodes of illness (respiratory, diarrheal and febrile illness; Primary Endpoint and Secondary Endpoints 1-5) in the preceding week (Appendix G). Surveys will be sent by email to all participants each Monday. Participants who have not completed the survey by Wednesday afternoon will be sent a request by email to complete the survey for the preceding week. Surveys will be sent weekly, for 26 weeks. A participant is considered to have completed the study one week after receipt of the final (26th) weekly survey for that participant's cohort.

As an incentive to enhance participant retention and response rates in weekly illness surveys, all participants who complete a weekly survey will be entered into a draw each week for a chance to win a EC\$25 gift voucher to a food/beverage vendor on the RUSVM campus. Selection of a winner each week will be done by computer-generated random sampling. The weekly winner will be notified by email in the week following the draw.

Clinically- and laboratory-confirmed episodes of study syndromes (Secondary Endpoints 6 & 7) will be collected by study personnel at RUSVM Student Health Services, as part of the

routine clinic visits and diagnostics. At the end of each 26-week observation period for each study cohort, data from that cohort will be compiled by the director of the RUSVM Student Health Services, anonymized to protect privacy and aggregated by study arm, before being sent to the Data Analyst who will conduct the analysis.

Occurrence of expected Adverse Events (Safety Endpoint 1) will be solicited in an online survey (Appendix H) sent to participants 3 days after receiving an injection (for dose 1, 2 and 3). Occurrence of unsolicited adverse events and serious adverse events (Safety Endpoint 2) will be captured by study personnel at RUSVM Student Health Services through completion of an Adverse Event form (Appendix I; See **Section 15.3, Identification of Adverse Events** for details).

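### Section 7.2 counts email-silent participants as withdrawn with no stated route back, and the semester break can supply two or three of the four missed surveys needed

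*Combined protocol and SAP*

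**What the plan says.** Two rules act on missed surveys.

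- **Section 7.1 (contact).** "Participants who fail to complete surveys for three consecutive weeks will be followed up and contacted". This leads to withdrawal only if the participant has withdrawn or wishes to.
- **Section 7.2 (lost to follow-up).** The rule applies to someone who "fails to complete a weekly survey for more than three consecutive weeks and is unable to be contacted by the study personnel". The only route named is the school address: "Contact will be by email". Then: "The participant will be considered unreachable if s/he does not respond after 3 emails". The spacing of the emails is not given. The consequence is: "At this point, s/he will be considered to have withdrawn from the study with a primary reason of lost to follow-up". The section does not say whether surveys continue, or whether a participant who answers later is reinstated.

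The setting matters because of the calendar. Section 5.1 states: "Each semester is 15 weeks, with a break of two or three weeks between semesters". Section 7 and its schedule run the 26 weekly surveys across that break into the next semester. Section 12 sends surveys by email each Monday with a midweek reminder, and the weekly draw is for a "gift voucher to a food/beverage vendor on the RUSVM campus".

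Three other places bear on the point. Section 6.5 keeps participants whose injections were halted in the weekly surveys. Section 14 specifies an intention-to-treat analysis of all events with weeks observed as the offset. Section 8 assumes average participation of 0.8 of the 26 weeks, estimated from weeks 3 to 9 of one summer semester, and re-estimates it in an internal pilot.

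**The concern.** With weeks observed as the offset, a temporary gap in reporting need cost only the weeks of the gap. Section 7.2 instead makes a run of silence the end of follow-up. The break is a foreseeable time for silence to begin: students may be away, and a campus voucher is of little use to them then. A student who comes back still blinded and willing to report has no stated way to do so.

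The weeks at stake lie in the second semester. They are needed for the 26-week comparison in Section 3.2.1 and for the exploratory duration-of-effect objective in Section 3.2.3. The rule is also stricter than the plan's own handling of participants who stop injections, who stay in the surveys.

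**Working it through.** **1. How many misses the break can supply.** More than three consecutive misses means at least four. A break holds two or three surveys. So a two-week break needs 4 − 2 = 2 further adjacent semester surveys missed, and a three-week break needs 4 − 3 = 1. A three-week break alone reaches only the Section 7.1 contact step.

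**2. How many surveys are forgone.** Survey 1 is sent in study week 3, so survey k is sent in study week k + 2. For a participant dosed in semester week 2, the schedule puts the break at study weeks 15–16, that is surveys 13–14 (13–15 for a three-week break). Surveys left after the fourth miss are 26 minus the last one missed:

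| Surveys missed | Surveys left | Share of 26 |
|---|---|---|
| 11–14 | 12 | 46% |
| 12–15 | 11 | 42% |
| 13–16 | 10 | 38% |
| 14–17 | 9 | 35% |

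The last row comes from counting back from the end weeks in Section 7 (week 11 of the following semester for a two-week break, week 10 for three), which starts the break at survey 14. The schedule table is broken in the text available, so this is treated only as a reason to give a range.

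The count is for on-schedule starters. Someone first dosed in week 12 meets the break 10 surveys earlier, at about survey 3; missing 3–6 would leave about 20.

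**3. The plan's sample size.** Inputs from Section 8: control rate μ0 = 2 per 26 weeks, rate ratio 0.75 so μ1 = 1.5, t = 0.8, k = 0.4, power 0.80; two-sided alpha 0.05 from Section 14.

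V = (1/t)(1/μ0 + 1/μ1) + 2k = (1/0.8)(0.5 + 0.6667) + 0.8 = 2.2583

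n per arm = (1.960 + 0.8416)² × V / (ln 0.75)² = 7.849 × 2.2583 / 0.08276 = 214.2, rounded up to 215.

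This gives 430 in total, as stated. Using t = 21/26 gives 213 per arm, so the plan's figure rests on 0.8, or 20.8 weeks.

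**4. Effect on power.** Let a share f of participants each lose 10 weeks. The documents give no value for f, so a range is assumed. Then t = (20.8 − 10f)/26 and power = Φ(√215 × 0.2877/√V − 1.960). For f = 10%, t = 19.8/26 = 0.7615, V = 2.332 and power = Φ(4.218/1.527 − 1.960) = Φ(0.802) = 0.789.

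| Assumed f | Mean weeks | Power at 215 per arm | N for 80% power |
|---|---|---|---|
| 0 | 20.8 | 0.802 | 430 |
| 5% | 20.3 | 0.795 | 436 |
| 10% | 19.8 | 0.789 | 444 |
| 20% | 18.8 | 0.775 | 458 |

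With 12 weeks lost instead of 10, 10% gives 0.786 and 20% gives 0.769.

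The charge of 10 weeks each is at the upper end. It supposes that every forgone survey would have been answered, and it is subtracted from an average that already allows for drop-out and non-response.

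**The case against.** The strongest reply is that the rule is hard to meet by accident. Silence that begins with the break reaches its third miss in the last week of a three-week break or the first week back after a two-week one. The Section 7.1 contact emails then go out around or after the return to campus. The student must also ignore at least one semester survey, the midweek reminders and three emails, and surveys can be answered from anywhere. All of that stands. It makes the affected share uncertain and probably modest.

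It can also be said that Section 7.2 only assigns a disposition and does not forbid reinstatement. That is literally true, so permanent exclusion is an inference. It is a natural one: the participant is deemed withdrawn, Section 9 offers withdrawn controls the vaccine after exit, and nothing in the plan describes a return.

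The internal pilot is a real mitigation. Its follow-up spans breaks, and it can raise the sample size. Its limit is that it uses the first 300 participants to complete the study. If withdrawn participants are left out of that set, average participation would be overstated; the plan does not say.

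A reader might infer that this loss biases the comparison between arms. The documents do not support that: participants are blinded and the rule is the same in both arms.

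**Conclusion.** The point holds as a cheap improvement. The rule ends follow-up for reasons the analysis does not require, at a cost of about 9 to 12 surveys for each on-schedule participant who falls silent around the break. Power stays between about 0.775 and 0.795 for assumed shares of 20% down to 5%, so power is not the main argument. Avoidable loss of second-semester follow-up is. The seven in-semester weeks behind the 0.8 participation figure contained no break and could not show any non-response during one.

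Two stronger readings should be avoided. The break by itself does not trigger withdrawal, since it holds at most three of the four surveys that must be missed. And no collected data are thrown away: nothing in the plan drops earlier weeks, and the offset keeps them.

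The conclusion rests on reading withdrawal in Section 7.2 as the end of weekly surveys, and on an assumed affected share.

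**What to change.** In Section 7.2:

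- Record a participant who meets the present criteria as 'not responding' rather than withdrawn.
- Keep sending the weekly survey through survey 26 to everyone who has not actively withdrawn consent or been unblinded.
- State that a still-blinded participant may resume.
- Assign 'lost to follow-up' only after survey 26.
- State that clinic-recorded Endpoints 6 and 7 continue to be counted for these participants. Nothing now says they stop, but it should be explicit.

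Leave the Section 7.1 contact trigger as it is. It only prompts outreach, and exempting break weeks from it would delay that outreach.

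The cost is protocol wording and continued automated emails. The downside is some intermittent missing weeks, which the weeks-of-observation offset handles.

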8 SAMPLE SIZE

The estimated number of participants needed to achieve the study's primary objective is 430 (215 in each group). The sample size was calculated using the approach for comparing two negative binomial rates based on true rates (Approach 2 in [17]), implemented using the function *power.nb.test* in package 'MKmisc' in R, and assuming the following parameter values:

- Alpha level = 0.05
- Targeted power = 0.8
- Event rate for control group = 2 (expected mean number of new CID episodes [composite primary endpoint] over 26 weeks)
- Rate ratio under alternative hypothesis = 0.75
- Average length of participation (accounting for drop-out and non-response) = 21 weeks (0.8 of 26-week observation period)
- Negative binomial dispersion parameter (k in [17]) = 0.4

The three nuisance parameters (average length of participation, event rate for control group and negative binomial dispersion parameter) were estimated from data collected over 7 weeks of a pilot study of rates of CID episodes in 90 RUSVM students (40 in 1st semester and 50 in 5th semester) from 21 May to 8 July, 2018 (weeks 3 through 9 of summer semester).

An internal pilot study will be done using data from the first 300 participants to complete the study. As the expected enrollment rate is <100 participants per semester, this will allow capture of seasonal variation in event rates (≥ 3 semesters in internal pilot study). The three nuisance parameters will be re-estimated from the internal pilot study data and the sample size recalculated, using a blinded sample size re-estimation method for count data [18, 19], which maintains required power without an increase in the type I error. The sample size will only be increased and not decreased on the basis of the internal pilot study (that is, if the recalculated sample size is smaller than the original sample size, the original sample size will still be used).

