14 STATISTICAL METHODS

The analysis of the primary endpoint and secondary endpoints 1-7 will be conducted after all randomized participants have completed the study (one week after receipt of the final weekly survey) or have withdrawn from the study, whichever occurs first. Primary analysis will be based on intention-to-treat analysis of all events (that is, not just occurrence of first events). The comparison of incidence rates of CID episodes (primary endpoint and secondary endpoints 1-7) between the treatment arms will be performed using a negative binomial regression model, which accounts for different lengths of observation period. Participants' number of CID episodes will be modelled as a function of treatment group, with the number of weeks of observation included as an offset in the model. This analytic model estimates the rate ratio, λ_t / λ_c , which quantifies the risk of CID episodes associated with rabies vaccination (λ_t) in comparison to placebo injection (λ_c). Statistical significance will be controlled at the 2-sided, 0.05 alpha level, and the estimated rate ratio compared with 1, assuming the following statistical hypothesis:

H_0 (null hypothesis): Rate ratio = 1

H_1 (alternative hypothesis) Rate ratio $\neq 1$

Treatment effect will be based on the coefficient in the model. Statistical significance at the pre-specified alpha level will be based on a Wald testing procedure. CID rates (primary

endpoint and secondary endpoints 1-7) for rabies vaccine and placebo, and the rate ratio, will be presented and will include 95% confidence intervals.

A detailed description of the statistical methods that will be used for the primary and secondary endpoints will be provided in a Statistical Analysis Plan (SAP).

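### N = 430 and its planned recalculation use only average participation, so uneven follow-up gives somewhat less power than stated, and a recalculation from the average cannot detect this

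*Combined protocol and SAP*

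**What the plan says.** Section 8 obtains 430 participants (215 per group) from a negative binomial rate comparison based on true rates. Its inputs are "Alpha level = 0.05", "Targeted power = 0.8", "Event rate for control group = 2 (expected mean number of new CID episodes [composite primary endpoint] over 26 weeks"), a rate ratio of 0.75, k = 0.4, and "Average length of participation (accounting for drop-out and non-response) = 21 weeks (0.8 of 26-week observation period").

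Average participation is the only one of its three nuisance parameters that describes follow-up. After an internal pilot of the first 300 to complete, "The three nuisance parameters will be re-estimated from the internal pilot study data and the sample size recalculated". The method is taken from references 18 and 19 and is said to preserve power. N may rise but not fall.

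Section 14 fits a negative binomial model "which accounts for different lengths of observation period", with each participant's own weeks as an offset. It also states that "Statistical significance will be controlled at the 2-sided, 0.05 alpha level".

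Several rules make follow-up uneven. Section 7.1 allows withdrawal at any time, and Section 11.3 ends participation at unblinding. Section 7.2 deals with people who miss more than three consecutive weeks and do not answer three emails: "At this point, s/he will be considered to have withdrawn from the study with a primary reason of lost to follow-up".

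**The concern.** The sample size formula treats every participant as observed for the same 0.8 of 26 weeks, while the analysis uses weeks that differ between participants. With k > 0 the two are not equivalent. A participant seen for all 26 weeks does not fully make up for one who leaves early, because repeated counts from one person share that person's underlying rate.

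The purpose of the internal pilot is to protect 80% power. It will re-estimate the mean of follow-up but not its spread. It can correct a wrong mean, a wrong k or a wrong event rate, but not this discrepancy.

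**Working it through.** **Inputs (Section 8, with sidedness from Section 14).** Two-sided alpha 0.05, power 0.80, r0 = 2 per 26 weeks, r1 = 2 × 0.75 = 1.5, k = 0.4, t = 0.8, 1:1 allocation. Then (1.960 + 0.842)² = 7.849 and (ln 0.75)² = 0.08276.

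**Reproducing 430.** With a common t, V = (1/t)(1/r0 + 1/r1) + 2k = 1.25 × (0.5 + 0.6667) + 0.8 = 2.258. Then n = 7.849 × 2.258 / 0.08276 = 214.2, so 215 per group and 430 in total. Power at 215 per group is Φ(√(215 × 0.08276 / 2.258) − 1.96) = 80.2%. Using 21/26 instead of 0.8 gives 213 per group, so the plan evidently used 0.8 for everyone.

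**Allowing t to vary.** Information on the log rate from a participant followed for fraction t is r·t/(1 + k·r·t). This is concave in t when k > 0, so by Jensen's inequality any spread around the same mean lowers its average. The variance term becomes

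V = 1/mean[r0·t/(1 + k·r0·t)] + 1/mean[r1·t/(1 + k·r1·t)].

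**Worked case: 60% complete and 40% drop out uniformly over 26 weeks (mean 0.6 + 0.4 × 0.5 = 0.8).** The mean information from a uniform drop-out is (1/k)[1 − ln(1 + kr)/(kr)].
- Control: 0.6 × 2/1.8 + 0.4 × 0.6632 = 0.9319.
- Vaccine: 0.6 × 1.5/1.6 + 0.4 × 0.5417 = 0.7792.
- V = 1/0.9319 + 1/0.7792 = 2.356, so n = 223.5 per group, N = 448, and power at 430 = 78.5%.

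**Range.** The mean is held at 0.8 throughout. The spread is an assumption, because the documents give none.

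| Pattern of follow-up | V | N for 80% | Power at 430 |
|---|---|---|---|
| Everyone exactly 0.8 (the plan) | 2.258 | 430 | 80.2% |
| Scattered missed surveys only (binomial, 26 weeks, 0.8) | 2.263 | 430 | 80.1% |
| 20% uniform drop-out, 0.889 response while in study (0.9 × 0.889 = 0.8) | 2.307 | 438 | 79.3% |
| 40% uniform drop-out | 2.356 | 448 | 78.5% |
| 20% give no data, 80% complete (extreme bound) | 2.458 | 468 | 76.7% |

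**Simulation check.** The planned Wald test with offset was simulated 3,000 times per pattern at 430. Power was 80.9% for fixed follow-up, 79.2% for 40% uniform drop-out and 76.2% for the extreme bound (Monte Carlo standard error 0.7 to 0.8 points). The drop from the first figure to the second agrees with the formula.

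**Does re-estimating k remove the problem?** No. If the pilot gave k = 0.8, the average-based formula would ask for 291 per group. Under 40% uniform drop-out 307 are needed, and 291 gives 77.9%. At k = 1.2 the figures are 366, 389 and 77.7%.

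**The case against.** A reader might infer that the recalculated N will be too small whatever the pilot shows. The documents do not support that, for two reasons.
- If losses are only scattered missed surveys, rounding up from 214.2 to 215 absorbs the effect.
- The rule against reducing N can cover it. At k = 0.35 the average-based formula gives V = 1.458 + 0.7 = 2.158 and N = 410, but 430 stands. Under 40% uniform drop-out 426 would be needed, and 430 gives 80.4%. At a control rate of 2.2 with k = 0.4, 430 gives 80.8% under the same drop-out.

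A reader might also take 77% as the realistic power. That figure needs a fifth of participants to return no survey and all the others to return all 26. Section 8 says its 0.8 covers both drop-out and non-response. Participants have consented in person and attended for an injection, and they receive reminders and a weekly prize draw. The figure is a bound, not a forecast.

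Nor do the rules impose automatic, permanent withdrawal for non-response. Section 7.1 has non-responders contacted and withdrawn only if they have left or wish to leave. Section 7.2 applies only to those who cannot be reached. Whether participants with no survey count towards the 430 is not stated.

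Materiality is a fair objection. The 40% drop-out case needs the same N as k = 0.45 with even follow-up, and the extreme bound the same as k = 0.5. The planning value of k came from 90 students over 7 weeks, so its own uncertainty may well matter more. But the internal pilot re-estimates k, whereas nothing planned addresses the spread of follow-up.

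Finally, references 18 and 19 were not available for this review. An implementation that uses individual times would avoid the problem. Section 8 does not say so; it names the average.

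**Conclusion.** The point holds as a small, one-directional inaccuracy in the stated formula. At a mean of 0.8 and the plan's other inputs, the cost is practically nil for scattered non-response, about 0.9 points of power (8 participants) for mixed loss, and about 1.7 points (18 participants) for 40% uniform drop-out. It cannot exceed about 3.4 points (38 participants). The direction follows from k > 0 alone; the size depends on a distribution of weeks that the documents do not give. It is not a reason to doubt the design or the planned analysis. It is worth correcting because the recalculation is meant to secure 80% power and the weekly surveys already supply the individual weeks it needs.

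**What to change.** In the blinded recalculation, replace (1/average t)(1/r0 + 1/r1) + 2k by 1/mean[r0·t/(1 + k·r0·t)] + 1/mean[r1·t/(1 + k·r1·t)], with the means taken over the individual observed fractions t of 26 weeks in the internal pilot.

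Define the pilot set in Section 8 as participants whose 26-week window has ended. Include those who withdrew and those who returned no survey (t = 0), and exclude those still under observation, whose final weeks are unknown. A set limited to people who stayed to the end would miss the spread that matters here.

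If the method in references 18 and 19, as implemented, already uses individual times, it is enough to correct Section 8 to say so. Until then, describe the power of 430 as about 78.5% to 80% under gradual drop-out or scattered non-response, depending on how follow-up is distributed.

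The cost is a small code change and a few sentences in Section 8. The price is a slightly less favourable power statement or a possible small rise in the recalculated N.
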